Treatment of Persistent Non-Severe Postpartum Hypertension

Document Date: September 24, 2021

NCT04349124

Purpose of the Study

Objective 1: Compare the average blood pressure of women with non-severe hypertensive disorders of pregnancy with and without treatment with nifedipine extended release at 1 week and 4 weeks postpartum.

We hypothesize that treatment with nifedipine extended release compared with no treatment will significantly reduce the average blood pressure at 1 week and 4 weeks postpartum in women with non-severe hypertensive disorders of pregnancy.

Objective 2: Determine the proportion of women with non-severe hypertensive disorders of pregnancy whose postpartum blood pressure at 1 week and at 4 weeks are normotensive (<130/80 mm Hg) per new American College of Cardiology and American Heart Association (ACC/AHA) guidelines with and without treatment with nifedipine extended release.

We hypothesize the proportion of women with non-severe hypertensive disorders of pregnancy who are normotensive per ACC/AHA guidelines at 1 week and 4 weeks postpartum will be higher among the women treated with nifedipine extended release compared women without treatment.

Background & Significance

BACKGROUND

a) Prevalence of postpartum hypertension

Hypertensive disorders of pregnancy include chronic hypertension, gestational hypertension, and preeclampsia. Chronic hypertension affects 1.5% of pregnancies; gestational hypertension and preeclampsia affect ~4-8% of pregnancies. The rate of hypertensive disorders of pregnancy is rising, in part, due increasing obesity and delayed childbearing leading to increased maternal age during pregnancy. Postpartum hypertension, which may be a new diagnosis or a continuation of a hypertensive disorder of pregnancy, affects ~2% of recently pregnant women. Of that 2%, gestational hypertension and preeclampsia make up 86% of postpartum hypertension cases.

b) Current treatment recommendations for postpartum hypertension

Severe range blood pressure $\geq 160/110$ mm Hg should be treated promptly in the postpartum period to reduce the risk of stroke. Acute severe postpartum blood pressure elevations are generally treated with one of three agents: intravenous labetalol, intravenous hydralazine, or oral immediate-release nifedipine. All three medications are considered safe and effective for management of severe postpartum hypertension and are considered 1st line therapy.

The treatment of persistently elevated non-severe blood pressure in the postpartum period is the interest of this proposal. In its newest hypertension in pregnancy guidelines, ACOG does not provide any specific guidelines for management of postpartum hypertension. The two most commonly used long-

acting oral anti-hypertensive used for postpartum hypertension are labetalol and extended-release nifedipine.

SIGNIFICANCE

- a) Postpartum hypertension is a significant contributor to severe maternal morbidity and maternal mortality

In the United States, there has been a recent focus on improving maternal mortality and severe morbidity. The maternal mortality rate in the United States has increased from 9.9 per 100,000 births in 1999 to 26.4 per 100,000 births in 2015, making it one of the highest maternal mortality rates among industrialized nations. This increase is most notable among non-Hispanic black women who had a mortality rate of 46 per 100,000 births in 2014. More common, however, is severe maternal morbidity (SMM), which increases the risk for maternal mortality. SMM can be explained as adverse outcomes of the process of labor and delivery that result in significant short-term or long-term consequences to a woman's health. The Center for Disease Control and Prevention defines SMM by 18 indicators commonly identified as peripartum complications. Severe maternal morbidity, like maternal mortality, has also significantly increased over the last 2 decades, from 49.5 per 10,000 births in 1993 to 144.0 per 10,000 births in 2014.

Hypertensive disorders of pregnancy such as preeclampsia and gestational hypertension are strongly associated with SMM including stroke, eclampsia, renal failure, and cardiomyopathy. Studies have shown that women with SMM are significantly more likely to have been diagnosed with a hypertensive disorder of pregnancy .

- b) ACOG does not provide robust guidance on the management of BP in the postpartum period

There is very limited data on which antihypertensive agent provides the best control of blood pressure in the postpartum period. One small randomized controlled trial (n=50) compared oral labetalol and nifedipine extended release for persistent postpartum hypertension in women with no previous therapy (17). The primary outcome was time to blood pressure control, which was not different between the two groups. Interestingly, blood pressure information was only available in 48% of women at 72 hours, 20% women at 1-2 weeks, and 16% of women at 4-6 weeks.

Outside of recommending treatment for postpartum blood pressure that is persistently above 150/100 mm Hg and using labetalol or nifedipine extended release, ACOG does not provide explicit guidance on initial dose of therapy, dose adjustments, duration of therapy, or parameters for discontinuing antihypertensive therapy. Additionally, many women who have gestational hypertension or preeclampsia, will have normalization of blood pressure without medical intervention. There is no data to evaluate spontaneous normalization of blood pressure as compared to women who are prescribed anti-hypertensive therapy for postpartum non-severe postpartum hypertension.

- c) ACC/AHA most recent blood pressure guidelines recommend blood pressure goal of <130/80 mm Hg in non-pregnant adults. No data on if women with hypertensive disorders of pregnancy are meeting this goal at their postpartum visit.

In 2017, the American College of Cardiology and American Heart Association Task Force on Clinical Practice Guidelines released new guidance for the diagnosis and treatment of hypertension which replaced the Joint National Committee 8 recommendations (JNC8) (18). Of note, hypertension was

classified into 4 stages, and normotensive blood pressure was defined as blood pressure < 130/80 mm Hg. Additionally, the use of blood pressure lowering medication is recommended for primary prevention of cardiovascular disease in adults with no history of cardiovascular disease when blood pressures are >140/90 mm Hg. If adults have a ≥10% risk of 10-year atherosclerotic cardiovascular disease (ACVD) or history of cardiovascular disease, blood pressure lower agents should be initiated if blood pressure ≥130/80 mm Hg. The 10-year ACVD risk will be unknown for most postpartum patients. However, many of our patients will have common risk factors for CVD. Pregestational diabetes affects 3-7% of pregnancies (19). Approximately 32% of reproductive age women ages 20-39 are obese (20). Increasing maternal age should also be a consideration for management of postpartum hypertension, given that older women are increased risk of adverse outcomes postpartum (21). Taken together, more research is needed to optimize treatment of postpartum hypertension especially in light of recent change management of non-pregnant adults.

Design & Procedures

This study is a pilot, open-label randomized controlled trial of postpartum women with hypertensive disorder pregnancy and non-severe, but elevated postpartum blood pressure. Potential study patients will be approached by a member of the study team during the postpartum period of the patient's delivery admission.

Exposures groups will be treated with nifedipine extended release and no treatment for non-severe postpartum hypertension. Patient will be randomized 1:1 fashion. The primary outcome of this study is average systolic blood pressure at 1 week postpartum. Blood pressure will be obtained at a 1-week blood pressure check. Alternatively, women will also be provided blood pressure cuffs and be able to check their blood at home at 1 week and submit result via text. Secondary outcomes will include average diastolic blood pressure at 1 week postpartum, average systolic and diastolic blood pressure at 4 weeks postpartum, percentage of patient with blood pressure < 130/80 mm Hg at 1 week and 4 weeks postpartum, method of feeding, ED/triage visits, increase in blood pressure medication at 1 week postpartum visit, initiation of blood pressure medication at 1 week postpartum visit for patients in the no treatment group, addition of 2nd blood pressure medication at 1 week postpartum visit, and hospital readmission.

Once informed consent has been obtained and the patient is deemed eligible for participation, patients will be randomized prior to discharge from Duke Birthing Center of Duke University Hospital. Subjects randomized to the treatment group will be provided the study drug (nifedipine extended release) at an initial dose of 30mg daily in 1-month supply. The control group will not receive any drug for blood pressure control, which is standard practice for patients with non-severe postpartum hypertension.

The control group will not receive any drug for blood pressure control, which is standard practice for patients with non-severe postpartum hypertension.

Dose adjustment of the treatment drug will be at the discretion of the obstetric provider, but a treatment algorithm will be provided for guidance. The use of an additional beta blocker (eg Labetalol) can be used at the discretion of the obstetric provider. This additional beta blocker is NOT a study drug

being investigated. Subjects in the no treatment group should not be started on medication at the 1-week postpartum visit unless blood pressure exceeds 160/110 mm Hg.

Subjects in both groups will be scheduled in the for a 1-week postpartum blood pressure check and routine 4 week postpartum visit in the Duke Perinatal Clinic as is standard of care at Duke for all patient with hypertensive disorders of pregnancy. Medication compliance in the treatment group will be assessed via validated questionnaire. As this is a pragmatic, pilot trial our control group is the current standard care for patients with persistent, non-severe postpartum hypertension instead of placebo.

Selection of Subjects

Inclusion criteria

- Antepartum diagnosis of gestational hypertension
- preeclampsia
- superimposed preeclampsia without antepartum chronic hypertension medication
- Delivery at 23 weeks or greater
- Persistent elevation in BP >12 hours postpartum ($\geq 140/90$ mm Hg) (2 or more documented BP)
- 18 years or older
- English speaking

Exclusion criteria

- Need for continuation of antepartum antihypertensive medication
- Contraindication of calcium channel blocker use
- Severe range (160/110 mm Hg) blood pressure requiring treatment >24 hours after delivery
- Requires a 2nd oral antihypertensive medication for blood pressure control inpatient
- Acute cardiomyopathy or heart failure
- Creatinine ≥ 1.5
- Blood pressure $<90/60$ within 24 hours of discharge

Study Interventions

The treatment group will provided with month supply of 30mg tablets of nifedipine extended release prior to discharge from the delivery admission. Dose increases in clinic will be at the discretion of providers, however a treatment algorithm will be provided for guidance.

The control group will not receive any medications at discharge. Providers will be instructed to only prescribe new blood pressure medication at subsequent postpartum visits if the blood pressure is in the sever range ($\geq 160/110$).

Both groups will be given a home blood pressure cuff prior to discharge with instructions for use. They will also be scheduled for a 1 week blood pressure check and 4 week postpartum clinic appointment which standard for these patients outside of this proposal.

Risk/Benefit Assessment

Risks for this study are minimal. Patients will provide information regarding blood pressures that should prompt contacting medical personnel. Side effects will also be assessed each postpartum visit. Nifedipine extended release may cause some, all or none of the side-effects listed below.

More likely

- Flushing
- Headache
- Dizziness
- Nausea
- Peripheral swelling

Less Likely

- Low blood pressure
- Muscle cramps
- Shortness of breath, wheezing
- Mood swings, nervousness
- Palpitations
- Itching
- Constipation
- Chest pain
- Special Considerations
- Nifedipine extended release is safe for women who are breastfeeding.

There is also a small risk of loss of confidentiality.

Participants in this study will be provided a home blood pressure cuff to check blood pressures at home which may provide more expedited medical attention for severely elevated blood pressures. Women with hypertensive disorders of pregnancy are at increased risk of developing hypertension later in life. All participants will be referred to primary care physician in order facilitate blood monitoring and health maintenance care outside of pregnancy.

Data Analysis & Statistical Considerations

Sample size calculation

Based on an expected average systolic postpartum blood pressure of 140 mmHg at randomization and standard deviation of 15 points, a sample size of 40 per group is needed to detect a 10 point change in systolic blood pressure with at least 80% power and alpha of 0.05. Assuming a study attrition rate of 20%, an additional 10 subjects per study group will be enrolled. The total goal enrollment is 100 participants (50 in each group) If subject recruitment is lower than expected, we calculated an alternative power calculation. Based on an expected average systolic postpartum blood pressure of 140mmHg at randomization and standard deviation of 15 points, a sample size of 21 per group is needed to detect a 15 point change in systolic blood pressure with 90% power and alpha of 0.05.

Assuming a study attrition of rate of 20%, an additional 4 subjects per study group will be enrolled. The total enrollment using this alternative power calculation 50 (25 in each group).

Statistical analysis plan

Baseline characteristics (demographics, comorbidities, and obstetric history) will be summarized with mean (standard deviation) or n (%) by treatment and control groups. The primary outcome will be presented and compared between two groups using a two-sample t-tests with equal variance. Normality assumption on empirical distribution of the primary outcome will be evaluated. If this assumption is violated, non-parametric Wilcoxon rank sum test will be used. Secondary outcomes will also be summarized and compared between groups using two-sample t-tests with equal variance for continuous outcomes or Chi-square tests for categorical outcomes. A planned, exploratory subgroup analysis will be performed to compare the treatment effect in participants with and without antepartum diagnosis of preeclampsia with severe features. Two-sided tests at $P<0.05$ will be considered statistically significant. All analyses will be performed in SAS 9.4 (SAS Institute Inc., Cary, NC). Statistical support will be provided by [name], MS and [name].

Data & Safety Monitoring

Subjects in both study groups will be provided with home blood pressure cuffs at discharge. They will be instructed to check blood pressure daily for 1 week postpartum and weekly thereafter. Subjects will be instructed to contact on-call OB providers if they have home blood pressure $< 90/60$ or $>/=160/110$. The contact for the OB triage, OB provider on call will be provided to patients. Subjects will be assessed for potential symptoms of nifedipine extended release at 1 week and 4 weeks postpartum visits. Patients will be referred to or given information for a primary care physician to for continued follow-up outside of the postpartum period.

A Data Monitoring Committee (DMC) will be created to perform regular and timely review of data semi-annually in order to identify early, significant benefit or harm for patients while the trial is in progress. Non-identified safety data will be communicated to the DMC who will then meet to review the data. The DMC will be composed of three faculty members within the Duke University Department of Gynecology and Obstetrics. Individuals who are investigators or co-investigators cannot be members. Members must have no financial, scientific, or other conflicts of interest with the study. All investigators understand that the DMC serves as additional human subject's protection, but does not supplant reporting of significant adverse events to the Duke IRB. The DMC may devise its own stopping rules, and if there are significant numbers of adverse events, the DMC will recommend continuation, modification, or termination of the study after each meeting. This recommendation will be communicated to the Principle investigator who is responsible for reviewing the recommendation and forwarding it to the IRB. All investigators understand that the DMC may recommend their own "stopping rule" if other events occur which indicate a significant risk to study subjects.

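### The objectives call the pregnancy disorder non-severe, while eligibility and the planned subgroup include preeclampsia with severe features; align the wording and, as an optional improvement, stratify and adjust on that factor

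*Combined protocol and SAP*

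**What the plan says.** **Objectives.** Under Purpose of the Study, Objective 1 is to "Compare the average blood pressure of women with non-severe hypertensive disorders of pregnancy with and without treatment with nifedipine extended release". Objective 2 and the two hypotheses name the same population. In all four statements the adjective non-severe belongs to the pregnancy disorder.

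**Design.** The title and the background on current treatment attach it to the postpartum pressure. So does Design & Procedures, which describes the sample as "postpartum women with hypertensive disorder pregnancy and non-severe, but elevated postpartum blood pressure".

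**Eligibility.** Selection of Subjects includes "preeclampsia" with no limit on severity. It also requires "Persistent elevation in BP >12 hours postpartum" at or above 140/90 mm Hg. The only exclusion based on severe-range pressure concerns the period after delivery: "Severe range (160/110 mm Hg) blood pressure requiring treatment >24 hours after delivery". Some other exclusions, such as creatinine of 1.5 or more or a need to continue antepartum antihypertensives, will remove some women with severe disease. None excludes an antepartum diagnosis of severe features as such.

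**Analysis.** The Statistical analysis plan states: "A planned, exploratory subgroup analysis will be performed to compare the treatment effect in participants with and without antepartum diagnosis of preeclampsia with severe features". The primary comparison is a two-sample t-test without covariates, with a Wilcoxon test if normality fails.

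**Allocation.** The text says "Patient will be randomized 1:1 fashion", before discharge. It names no stratification factor, blocking or sequence method.

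**The concern.** Objectives and hypotheses state what the trial claims to test, and a report usually takes its conclusion from them. Read literally, they restrict the claim to non-severe disorders, and the severe-features subgroup in the analysis plan would be empty. A conclusion in those words would claim an effect for one population on evidence from a mixed one.

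A second, lesser matter follows. Antepartum severe features is the only subgroup factor the plan names, and it is known before randomisation. Yet the documents describe nothing, in allocation or in the primary analysis, that balances the arms on it or adjusts for it. With 50 to 100 women, a chance imbalance could move the primary difference somewhat and leave few women with severe features in one arm.

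**Working it through.** **1. The wording, side by side**

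| Place | What is non-severe | Can a woman with antepartum severe features be included? |
|---|---|---|
| Objectives 1 and 2, both hypotheses | The pregnancy disorder | No, read literally |
| Title, background, Design & Procedures | The postpartum pressure | Yes |
| Selection of Subjects | Postpartum pressure only | Yes |
| Statistical analysis plan | Not stated | Yes, a subgroup is planned |

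The objectives and hypotheses are out of line with the rest. No arithmetic is needed for this part.

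**2. The plan's sample sizes**

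No stated figure depends on this point; the sizes only set the scale.
- Main: difference 10, SD 15, two-sided 0.05, 80% power. n = 2 × (1.96 + 0.8416)² × 15² / 10² = 35.3, so 36 per group (37 by the t-test). At the stated 40 per group, power is 84.6% (normal) or 83.8% (t), which agrees with at least 80%. Enrolment is 40 / 0.8 = 50 per group.
- Fallback: difference 15, SD 15, 21 per group. Power is 90.0% (normal) or 88.5% (t). Stated enrolment is 25 per group.

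**3. Chance imbalance on severe features**

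The documents do not give the share with severe features. Assume 30%: 15 of 50 women, or 30 of 100.

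| Allocation model | 15 women split 10:5 or worse | 30 women split 20:10 or worse |
|---|---|---|
| Arms fixed equal (hypergeometric) | 2 × P(X ≤ 5) = 21.7% | 2 × P(X ≤ 10) = 4.9% |
| Coin flip (binomial, p = 0.5) | 2 × P(X ≤ 5) = 30.2% | 2 × P(X ≤ 10) = 9.9% |

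Varying the assumed share from 20% to 50%, with independent binomial counts in each arm, gives:
- gap of at least 10 percentage points: 37–48% at 25 per arm, 26–37% at 50 per arm;
- gap of at least 20 percentage points: 11–20% at 25 per arm, 2–6% at 50 per arm.

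**4. Effect on the primary difference**

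Shift = prognostic effect × difference between arms in the share with severe features. A 10:5 split at 25 per arm gives 10/25 − 5/25 = 0.20. The prognostic effect is not in the documents; assume 3 to 8 mm Hg.
- 0.20 × 3 = 0.6 mm Hg and 0.20 × 8 = 1.6 mm Hg.
- The matching target is the fallback's 15 points: 0.6/15 = 4% and 1.6/15 = 11%.
- The standard error at 25 per arm is 15 × √(2/25) = 4.24 mm Hg, so even 1.6 is only 0.38 of one standard error.

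A 20:10 split at 50 per arm gives the same 0.20, hence the same 0.6 to 1.6 mm Hg. There the target is 10 points and the standard error is 15 × √(2/50) = 3.0. That split has about a 5% chance with equal arms.

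At 30% and 8 mm Hg, the factor explains 0.3 × 0.7 × 8² / 15² = 6% of the outcome variance, so adjustment would add little precision.

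**5. The subgroup contrast when balanced**

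SE = 15 × √(2/(np) + 2/(n(1 − p))), with n per arm and share p. For n = 40 and p = 0.3, SE = 15 × √(2/12 + 2/28) = 7.32 mm Hg. Power for a 10 mm Hg difference in effect is Φ(10/7.32 − 1.96) = 28%. Over p = 0.2 to 0.5, power is 22–32% at 40 per arm and 14–19% at 21 per arm. These figures already assume perfect balance.

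**The case against.** **The intent is plain.** The title, background, design section, eligibility criteria and planned subgroup all point to non-severe postpartum pressure. On this view the objectives contain a misplaced adjective, and eligibility decides who is analysed. That is right about intent. A reader might infer from the mismatch that the trial enrols the wrong women or that eligibility is in error; the documents do not support this. What remains is that four statements of purpose still describe a narrower population than the one enrolled.

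**Stratification is a preference.** Simple 1:1 allocation with an unadjusted t-test is valid, because chance imbalance is already reflected in the standard error and the type I error rate. The trial calls itself a pilot, and the subgroup is labelled exploratory. All of this stands. A reader might infer that the primary result would be biased or invalid without stratification; it would not.

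**The absence of balancing is inferred from silence.** This also stands. The documents give the ratio and no method, so a stratified or blocked list may exist undescribed. It cannot be asserted that the arms are unbalanced by design.

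**Stratifying would not rescue the subgroup.** Correct: its power is low even with perfect balance.

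**Conclusion.** The wording mismatch is real and is settled by the text alone. It affects what the trial may claim, not who is enrolled or whether any test is valid. It is minor but should be corrected before a conclusion is drawn in the words of the objectives.

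Stratifying and adjusting is a cheap improvement, not the repair of an error. Its size rests on two assumptions that the documents neither supply nor contradict: the share with severe features and the prognostic effect on systolic pressure. The benefit is greatest in the 50-woman fallback. There, a 2:1 or worse split is fairly likely, but its effect on the difference is still small beside both the standard error and the 15-point target. It would be wrong to set that fallback shift against the 10-point target, which belongs to the 100-woman design.

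**What to change.** 1. **Wording.** In Objectives 1 and 2 and both hypotheses, define the population as women with hypertensive disorders of pregnancy, including preeclampsia with severe features, and non-severe elevated postpartum blood pressure. This changes four statements and leaves eligibility and sample size as they are.

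2. **Allocation and analysis (optional).** Stratify the 1:1 list by antepartum severe features (yes or no) in permuted blocks, and include that factor in the primary comparison, for example in a linear model with arm and stratum. If a stratified scheme already exists, describing it settles the allocation part. If the sponsor prefers not to stratify, prespecified adjustment for the factor remains available. The cost is a two-stratum list, one model term and one more item to enter at randomisation; the sample size does not change.

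3. **Subgroup.** Keep it labelled exploratory, whatever is decided on stratification.

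### Three 1-week medication outcomes fall under a blanket between-arm test, although one is defined in a single arm and two presuppose a drug that controls are not given at discharge; report them within arm.

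*Combined protocol and SAP*

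**What the plan says.** Design & Procedures lists three medication outcomes at the 1-week visit among the secondary outcomes:

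- "increase in blood pressure medication at 1 week postpartum visit", with no arm or denominator stated;
- "initiation of blood pressure medication at 1 week postpartum visit for patients in the no treatment group", which names one arm;
- "addition of 2nd blood pressure medication at 1 week postpartum visit, and hospital readmission", where the second-drug item again carries no arm or denominator.

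The Statistical analysis plan section says that secondary outcomes are summarised and "compared between groups using two-sample t-tests with equal variance for continuous outcomes or Chi-square tests for categorical outcomes". Two-sided tests below 0.05 "will be considered statistically significant". No outcome is exempted.

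The arms start from different positions and follow different rules. The nifedipine arm leaves hospital on study drug. Under Study Interventions, "The control group will not receive any medications at discharge". For nifedipine patients, "Dose adjustment of the treatment drug will be at the discretion of the obstetric provider", with an algorithm as guidance, and adding a beta blocker is also left to the provider. For controls, "Providers will be instructed to only prescribe new blood pressure medication at subsequent postpartum visits" when the pressure is in the severe range.

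**The concern.** A between-group test needs an outcome that patients in both groups can have. Initiation is defined only for controls, so the analysis rule cannot be applied to it as written. Dose increase and second-drug addition need an existing drug, and a control managed per protocol reaches the 1-week visit without one.

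The zeros, or near-zeros, also fall in opposite arms. If nifedipine patients are coded as not initiating, initiation can only count against no treatment. Increase and addition count almost only against nifedipine. Both directions are fixed before any data are collected. A p-value below 0.05 could be reported as a treatment difference and one above 0.05 as no difference, and neither reading would be supported.

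**Working it through.** The documents state no figure for these outcomes, so there is none to reproduce. The check has two parts.

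**1. Can the event occur in each arm?**

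| Outcome at 1 week | Nifedipine arm | No-treatment arm |
|---|---|---|
| Initiation | Outside the stated definition | Possible; severe-range pressure required |
| Dose increase | Possible; provider discretion with algorithm | Only if a drug was started before the visit |
| Second drug added | Possible; provider discretion | Only if a drug was started before the visit |

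The pre-visit route for controls is real. Data & Safety Monitoring tells patients to call the on-call provider about severe home readings, and that call could lead to a prescription. Increase and addition are therefore largely, but not strictly, one-arm outcomes. Initiation is strictly so.

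**2. What would the planned test do if one arm has zero events?**

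Inputs from the Sample size calculation section: 40 per group evaluable (50 enrolled) in the main plan, and 21 per group (25 enrolled) in the alternative. From the Statistical analysis plan section: chi-square, two-sided 0.05.

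For k/n against 0/n, the uncorrected Pearson statistic on 1 degree of freedom reduces to X² = 2nk / (2n − k).

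| n per group | k = 3 | k = 4 |
|---|---|---|
| 40 | 240/77 = 3.12, p = 0.078 | 320/76 = 4.21, p = 0.040 |
| 21 | 126/39 = 3.23, p = 0.072 | 168/38 = 4.42, p = 0.036 |
| 50 | 300/97 = 3.09, p = 0.079 | 400/96 = 4.17, p = 0.041 |
| 25 | 150/47 = 3.19, p = 0.074 | 200/46 = 4.35, p = 0.037 |

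Four events in one arm is the threshold at every planned size.

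The documents give no event rates, so the rates below are assumptions. The chance of p < 0.05 is P(X ≥ 4) with X ~ Binomial(n, r):

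| Assumed one-arm rate r | n = 40 | n = 21 |
|---|---|---|
| 5% | 0.14 | 0.02 |
| 10% | 0.58 | 0.15 |
| 20% | 0.97 | 0.63 |

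The result depends on how common the event is in one arm and on n. Nothing measured in the other arm enters it.

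**Sensitivity.** If the near-zero arm has one event instead of none, six are needed in the other arm at both sizes:

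- n = 40: 6 v 1 gives X² = 80(6×39 − 1×34)² / (40×40×7×73) = 3.91, p = 0.048; 5 v 1 gives p = 0.090.
- n = 21: 6 v 1 gives p = 0.038; 5 v 1 gives p = 0.078.

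Fisher's exact test against zero events needs six at 40 per group and five at 21. At an assumed 10% rate, the chance of p < 0.05 then falls to 0.21 and 0.05.

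**The case against.** The strongest reply is that initiation already names its population. The natural reading is a one-arm descriptive item, and no sensible analyst would enter nifedipine patients as zeros. For the other two outcomes the text sets no arm restriction, and a control treated before the visit could have either event, so a test can be computed; on this view the gap is only an unstated denominator. The four-event threshold holds only with exactly zero events in the other arm. Expected counts of two per arm are also too small for chi-square, and an exact test would be harder to pass. Finally, prescribing in an open-label pragmatic pilot differs by arm by design, and that alone does not make a medication outcome unreportable.

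Much of this is fair. The case is strongest for initiation and is an inference from the design for the other two. The probabilities are illustrative and would be lower under an exact test or with a few control events. For initiation they apply only under the zero coding. But the written rule has no exception, and a decision to leave out a test should be made before the data are seen. Being able to compute a test does not make it interpretable when one count is held near zero by design. An exact test moves the threshold and leaves the comparison as it was. The proposal also keeps the outcomes reportable; it removes only the between-arm p-value.

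**Conclusion.** The concern holds, as a minor point. Followed as written, the plan gives either no test (initiation) or a p-value driven by outcome construction and arm-specific prescribing rules (increase and addition). One outcome is strictly one-arm and two are largely so. With zero events in the other arm, four events suffice for nominal significance at every planned sample size. How likely that is runs from 0.02 to 0.97 across the assumed rates and the two evaluable sizes, so the actual risk cannot be pinned down from the documents.

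The primary analysis, the sample size and the arm-neutral secondary outcomes (mean pressures, the proportion below 130/80, ED/triage visits, readmission) are unaffected.

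**What to change.** Add to the Statistical analysis plan section:

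*Initiation of, increase in, and addition of a second blood pressure medication at the 1-week visit will be summarised within arm only (n/N, %, exact 95% CI), with no between-arm test; initiation applies to the no-treatment arm.*

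For scale, 4/40 would be reported as 10% (exact 95% CI 2.8% to 23.7%).

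If a between-arm medication outcome is wanted, define one that can occur in both arms: any antihypertensive started, increased or added at the 1-week visit. Report it as a risk difference with 95% CI, and state that the prescribing rules differ by arm, so that it partly measures those rules.

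One related inconsistency affects who counts as an initiation. Design & Procedures lets controls start a drug when pressure is above 160/110, whereas Study Interventions says at or above it. The two passages must be reconciled.

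The cost is one or two sentences and no new data, since the combined outcome uses the three items already listed. The three outcomes lose their between-arm p-values.
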